 - for Day 14 (or last assessment on Day x), if the symptom meets definition of alleviation, and day 13 (or Day x -1) also meets the definition of alleviation, then it is considered as confirmed. One missing day is allowed for the confirmation of Day 14 or last assessment, i.e if day 13 (or Day x-1) is missing and Day 12 (or Day x-2) meets the definition of alleviation, then it is considered as confirmed.

Examples:

Example	Day														Alleviation for a symptom on day	
	1	2	3	4	5	6	7	8	9	10	11	12	13	14		
1	2	2	2	1	1	1	0	0	0	0	0	0	0	0	4	baseline 2 or higher needs to be 1 or 0
2	2	2	2	0	1	1	0	0	0	0	0	0	0	0	4	baseline 2 or higher needs to be 1 or 0
3	2	2	2	0	2	1	1	0	0	0	0	0	0	0	6	day 4 is not confirmed
4	3	2	2	1	1	1	0	2	1	1	0	0	0	0	4	still on day 4 if worsen after confirmation
5	1	1	1	0	0	0	1	0	1	1	0	0	0	0	4	Worsening on day 7
6	1	1	1	1	0	0	0	0	0	0	0	0	0	0	5	baseline 1 needs to be 0
7	2	2	2	1	.	1	0	0	0	0	0	0	0	0	4	allow one missing
8	2	2	2	1	.	.	1	1	.	0	0	0	0	0	7	day 4 is not confirmed if there are two or more days' response missing, re-start the check for confirmation
9	2	2	2	2	2	2	2	2	4	2	2	2	2	1	14	censor
10	2	2	2	2	2	2	2	2	2	2	2	2	1	.	13	censor
11	2	2	2	2	2	2	2	2	2	2	2	2	1	1	13	Confirmed on day 13 and 14
12	2	2	2	2	2	2	2	2	1	9	censor
13	2	2	2	2	2	2	2	2	1	1	9	Confirmed on day 9 and 10

Yellow –Confirmed alleviation, Tan – Not confirmed, Blue - Worsening

3. Alleviation of baseline symptoms for a participant

The alleviation status for a participant at each visit is

- Yes, if all confirmed baseline symptom alleviation status are Yes.
- if > 25% of symptoms are missing, then alleviation status is No, else ignore missing.
- No, if any baseline symptom alleviation status is No.

4. Tim to alleviation of baseline symptoms

First day of participant level alleviation status equals Yes. If a participant has not achieved symptom alleviation at last FLUPRO assessment, the participant will be censored at the date of last FLUPRO assessment. For symptom alleviation of a domain, the last assessment date is only among those baseline symptoms within the domain.

23) Covid-19 medications include: Chloroquine, Hydroxychloroquine, IV remdesivir, Bamlanivimab, Casirivimab/Imdevimab, Molnupiravir, Lopinavir-ritonavir, and Ribavirin.

Additional medication may be included during final review of Concomitant medications prior to data finalization and documented in a separate programming specification.

24) Glucose

Fasting is not required per protocol for collecting Glucose sample, mixed fasting Glucose and non-fasting Glucose results are presented in the dataset. Lab abnormality for Glucose will be summarized as follows:

- if fasting glucose is collected at baseline, max TE lab toxicity grade is selected for post-baseline fasting glucose, max post-baseline toxicity grade (i.e. not TE toxicity grade) is selected for the post-baseline glucose regardless fasting status.
- if non-fasting glucose is collected at baseline, TE lab toxicity grade is selected for post-baseline non-fasting glucose, max post-baseline toxicity grade is selected for the post-baseline glucose regardless fasting status.
- Max TE lab toxicity grade for fasting glucose and non-fasting glucose, max post-baseline toxicity grade for fasting glucose and non-fasting glucose will be summarized separately in the lab abnormality table.
- In the any TE lab toxicity section of the lab abnormality table, max post-baseline toxicity grade will be included.

GS-US-553-9020-SAP-v1.0

ELECTRONIC SIGNATURES

Signed by	Meaning of Signature	Server Date (dd-MMM- yyyy hh:mm:ss)
PPD	Biostatistics eSigned	07-Jun-2021 15:06:42
PPD	Clinical Research eSigned	07-Jun-2021 19:02:43

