3.8. Analysis Visit Windows

3.8.1. Definition of Study Day

Study Day 1 is defined as the first dosing date of study drug.

Study Days are calculated relative to Study Day 1 and derived as follows:

- For postdose study days: Assessment Date – First Dosing Date + 1
- For days prior to the first dose: Assessment Date – First Dosing Date

Therefore, **Study Day 1/ First Dose Date** is the day of first dose of study drug administration, as recorded on the Study Drug Administration eCRF form.

Last Dose Date is defined as the maximum, nonmissing, nonzero dose end date of treatment recorded on the Study Drug Administration eCRF form with “Study Drug Permanently Withdrawn” box checked for participants who prematurely discontinued or completed study drug according to the Study Drug Completion eCRF.

Last Study Date is the latest of the study drug start dates and end dates, the clinic visit dates, FLU-PRO questionnaire collection date, and the laboratory visit dates, including the 28-day follow-up visit date, and the death date (if applicable, only for participants who prematurely discontinued study according to the Study Completion eCRF).

Baseline value is defined as the last value obtained on or prior to the first dose date (and time, if available) unless otherwise specified (see Section [3.8.3](#)).

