6.2.1. Analysis of Secondary Efficacy Endpoints

The FAS will be the primary analysis set for hospitalizations, MAVs and FLU-PRO questionnaire analyses. The mFAS will be the primary analysis set for SARS-CoV-2 viral load analyses.

Composite Endpoint of All-Cause MAVs or All-Cause Death by Day 28

The proportion of participants with all-cause MAVs or all-cause death by Study Day 28 will be estimated using Kaplan-Meier methods by treatment group and compared among 3 treatment groups in Part A and Part B and between the 2 treatment groups in Part C using a log-rank test.

If participants have no event by Study Day 28, participants will be censored at date of earlier of Study Day 28 and last study day. If a participant has a MAV first and then dies, then date of the MAV and status will be used for this participant.

Composite Endpoint of COVID-19 Related MAVs or All-Cause Death by Day 28

The proportion of participants with COVIS-19 related MAVs or all-cause death will be analyzed using the same method as used for composite endpoint of all MAVs or all-cause death by day 28.

In addition, a summary by pooled RDV and Pooled PTM may be provided and compared using CMH method including Part as strata in the model.

Proportion of participants hospitalized by Day 28

The proportion of participants with all-cause hospitalization (ICU, non-ICU, or unknown ward from Hospitalization/MAVs CRF) by Study Day 28 will be estimated using the Kaplan-Meier method and compared among treatment groups using a log-rank test. The time to all-cause hospitalization is defined using the first hospitalization date by Study Day 28, depending on which happens first. If participants have no event by Study Day 28, participants will be censored at date of earlier of Study Day 28 and last study day/death.

Time to Negative SARS-CoV-2 PCR

Negative SARS-CoV-2 PCR based on RT-PCR viral load is defined as:

- (1) the results reported as ‘No SARS-CoV-2 detected’, AND
- (2) two consecutive negative results, or negative at last available sample for participants who completed or discontinued from study.

The time to negative SARS-CoV-2 PCR is defined (in days) as the number of days to first confirmed negative:

First date of two consecutive dates achieving negative result – First dose date +1.

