7.1.6.2. Incomplete Dates

If the onset date of the AE is incomplete and the AE stop date is not prior to the first dosing date of study drug, then the month and year (or year alone if month is not recorded) of onset determine whether an AE is treatment emergent. The event is considered treatment emergent if both of the following 2 criteria are met:

- The AE onset is the same as or after the month and year (or year) of the first dosing date of study drug, and
- The AE onset date is the same as or before the month and year (or year) of the date corresponding to 30 days after the date of the last dose of study drug

An AE with completely missing onset and stop dates, or with the onset date missing and a stop date later than the first dosing date of study drug, will be considered to be treatment emergent. In addition, an AE with the onset date missing and incomplete stop date with the same or later month and year (or year alone if month is not recorded) as the first dosing date of study drug will be considered treatment emergent.

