- i. The month and year (or year) of onset date is the same as or after the month and year (or year) of the first dose of study drug, and
- ii. The month and year (or year) of the onset date is the same as or before the month and year (or year) of the 30th day after the date of the last dose of study drug, and
- iii. End date is as follows:

The (complete) end date is on or after the first dose date, or

The month and year (or year) of end date is the same or after the month and year (or year) of the first dose of study drug, or

End date is completely missing

Events with Completely Missing Onset Date

An AE with a completely missing onset date is defined as TEAE if end date meets any of the 3 criteria specified above.

10) The precision in reporting numerical values should be as follows:

Raw measurements will be reported the same as the data captured electronically or on the eCRF for all.

Standard deviation and standard error will be reported to one more significant decimal place than the raw measurement.

Mean, median, minimum, Q1, Q3, and maximum will be reported to the same number of decimal places of the raw measurements.

Exceptions may be considered; for example, if more than 4 significant digits are provided for the measurement.

Precision for derived parameters will be kept as 8 decimals and in listings 2 decimals will be kept.

Precision for derived parameters as follows:

Parameters	Decimal Places
log 10 of SARS-CoV-2 viral load	2
Time-weighted average change in SARS-CoV-2 viral load	2
BMI	2

- 11) Last dose date is not expected to be missing. However, if last dose date is missing, it will be imputed using the maximum of non-missing, non-zero dose, study drug start and stop dates.
- 12) Incomplete death dates will be imputed as the maximum of the study drug start dates (lasfdt), study drug end dates (lasldt), clinic visit dates (lvis28dt), laboratory visit dates (llab28dt), including the 28-day follow-up visit date plus 1, ie dthdt = $\max(\text{lasfdt}, \text{lasldt}, \text{lvis28dt}, \text{llab28dt}) + 1$.
- 13) Censoring rules

Time to hospitalization: If a participant prematurely discontinues from the study prior to Day 28 or the hospitalization status is missing, the participant is censored at last study date or day 28 whichever is earlier.

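### SAP Appendix 2 item 12 ignores a recorded month or year when it imputes a death date, so a death the data place after Day 28 can count as a by-Day-28 event

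*SAP*

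**What the plan says.** Item 12 of SAP Appendix 2 reads "Incomplete death dates will be imputed as the maximum of the study drug start dates (lasfdt), study drug end dates (lasldt" and continues with the last clinic visit date (lvis28dt) and last laboratory date (llab28dt), "including the 28-day follow-up visit date plus 1". It makes no distinction between a date with a known month, a date with only a year, and a date wholly missing. No other section overrides it or gives a sensitivity analysis for it.

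Four other parts of the SAP bear on it:

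- **Section 3.8.1, Last Study Date.** This uses a wider set of dates: "FLU-PRO questionnaire collection date, and the laboratory visit dates, including the 28-day follow-up visit date, and the death date". The FLU-PRO diary date is in that list but not in item 12.
- **Section 7.1.6.2, partial adverse event dates.** Here "the month and year (or year alone if month is not recorded) of onset determine whether an AE is treatment emergent". Section 7.4 likewise uses month and year for partial medication dates.
- **Section 6.2.1, composites.** "The proportion of participants with all-cause MAVs or all-cause death by Study Day 28 will be estimated using Kaplan-Meier methods". Those without an event are handled as follows: "participants will be censored at date of earlier of Study Day 28 and last study day". A MAV that precedes death supplies the event date. The COVID-19-related composite, which also includes all-cause death, uses the same method.
- **Section 7.1.7, treatment-emergent death.** The window runs from first dose to last dose plus 30 days, inclusive.

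**The concern.** An imputation rule for a partial date should not produce a date that the recorded part excludes. Item 12 can. It places the death one day after the last drug, visit or laboratory record even when the case report form shows a later month. Death is a component of both Day 28 composites and defines treatment-emergent death, so the imputed date can decide whether the participant is an event.

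Two lesser effects follow from the same wording. Because diary dates are left out, an imputed death can fall before diary entries the participant completed. And because the 28-day follow-up date is included, and that follow-up may be by telephone (Protocol 6.5 and 6.8), a follow-up record made after the death can push the imputed date past Day 28 and past the recorded month.

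**Working it through.** The plan states no figure on this point, so there is none to reproduce.

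**Inputs.** Study day = date − first dose date + 1 (SAP 3.8.1). Composite cut-off: Study Day 28 (SAP 6.2.1). Diary: Days 1 to 14 (SAP 3.8.2). Day 28 follow-up window: ± 5 days, so Days 23 to 33 (Protocol 6.5, 6.8). Arm sizes: 36/3 = 12 in Parts A and B; 80 × 3/4 = 60 RDV and 80 × 1/4 = 20 PTM in Part C (SAP 1.3). Let L be the study day of the latest drug, visit or laboratory record. Item 12 gives L + 1.

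**1. Into the composites.** L + 1 ≤ 28 whenever L ≤ 27. Every incompletely dated death with L from 1 to 27 therefore becomes an event by Day 28, whatever month is recorded. If that month begins after Day 28, the recorded data contradict the result.

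*Example.* Take Day 1 as 24 January 2021. This is illustrative; Appendix 2 item 17 gives it as the first Part C screening date.

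- Last visit Day 14 = 6 February.
- Death recorded as March 2021: 1 March = Day 37, 31 March = Day 67.
- Item 12 gives 7 February = Day 15, an event by Day 28.
- Last dose Day 5 = 28 January; plus 30 days = 27 February = Day 35. Day 15 is inside the treatment-emergent window, while Days 37 to 67 are outside it.

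**2. Out of the composites.** Let L run from 1 to 33 and the true death day D from L to 60, so that every record is dated on or before the death. Only one pair gives L + 1 > 28 with D ≤ 28: last contact and death both on Day 28. Otherwise a record dated Day 28 or later must have been made after the death.

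*Example.* First dose 1 February 2021, death recorded as February 2021 (28 February = Day 28). A follow-up on Days 28 to 33 reports the death and is entered as the visit. Item 12 gives Days 29 to 34, that is 1 to 6 March: past Day 28 and outside the recorded month.

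**3. Diary dates.** With last diary day F ≤ 14, adding F gives max(L, F) + 1. Where F exceeds L, this is at most Day 15, so Day-28 status changes in no case. Timing does change. With L = 7 and diaries to Day 14, item 12 gives Day 8, before six diary entries (Days 9 to 14); with the diary date it gives Day 15. This assumes the Part C Day 14 call is not counted as a clinic visit, which the SAP does not settle.

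**4. When the recorded month spans Day 28.** For a first dose on d February 2021, 1 March is Study Day 30 − d. For d = 1 that is Day 29. For d = 2 to 28 it is Day 28 or earlier, so a death recorded as March 2021 is not placed after Day 28 by its month alone.

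**5. Size.** One misplaced death, with no earlier censoring in the arm: 1/60 = 1.7 points, 1/20 = 5.0 points, 1/12 = 8.3 points.

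**The case against.** The strongest reply is that item 12 is a last resort that may never be used. A death is a serious adverse event, reported within 24 hours of the investigator's knowledge (Protocol 7.1.2, 7.4.1.1), and hospital or autopsy reports may be requested (Protocol 7.4.1). Serious events are reconciled with the safety database (SAP 7.1.5), and queries are resolved before the final analysis (SAP 2.2). A MAV before the death fixes the event date regardless. All of this stands, and it limits how often the rule matters. It does not make the rule right when it is used.

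It can also be said that Section 7.1.6.2 classifies adverse events rather than imputing dates, so there is no contradiction between the two rules. That is correct. The comparison shows only that the SAP uses a recorded month elsewhere. The fault in item 12 is that it can contradict the participant's own recorded data.

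Three stronger readings are tempting and not supported:

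- A reader might infer that omitting diary dates moves deaths across Day 28. It cannot, because the diary ends on Day 14.
- A reader might infer that the rule errs equally in both directions. It gives nearly the earliest possible date, so the error runs mainly inward. The outward route needs the conditions in step 2, and nothing in the documents says that a call with someone else is entered as the participant's visit.
- A reader might infer that any death recorded in the month after dosing is misclassified. Step 4 shows that often the month alone cannot say.

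**Conclusion.** The point holds in a limited form. Item 12 is wrong as written because it can assign a date that the recorded month or year rules out. The clear harm is inward: recorded month beginning after Day 28, last drug, visit or laboratory date on Day 27 or earlier, and no earlier qualifying MAV. Such a death enters both Day 28 composites. It is also miscounted as treatment-emergent, but only if the month begins after last dose plus 30 days as well. The diary omission affects timing and sequence only, and the outward route is less common.

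This is a minor point. It requires an incompletely dated death in a small outpatient trial, after the safeguards above. The sizes of 1.7, 5.0 and 8.3 points are per single death at the planned arm sizes; the documents give no expected number of such deaths.

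**What to change.** Replace item 12 with the following:

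- If a month and/or year is recorded, impute the later of (i) the first day of that period and (ii) max(lasfdt, lasldt, lvis28dt, llab28dt, last FLU-PRO date) + 1. Cap the result at the end of the recorded period and, if available, at the date the death was reported.
- Exclude from the maximum any visit record dated after the death was reported, or known not to be contact with the participant.
- Use the maximum + 1 alone only when the death date is wholly missing.
- State that when the recorded month spans Day 28 the imputed date remains a convention, and flag any such death in the listing.

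On the examples, March 2021 becomes 1 March = Day 37, outside both the composites and the Day 35 window. February 2021 is capped at 28 February = Day 28 at the latest, and so is counted.

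The cost is SAP wording and a few lines of derivation code. The month bound and the diary date use data already held. The exclusion of contacts with someone else is conditional, because the documents do not show that the eCRF records who was reached on a call. If the SAP has already been finalized, Section 1 requires the change to be documented in the clinical study report.

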1.3. Study Design

This is a randomized, blinded, placebo-controlled, multicenter study to evaluate the safety, efficacy, and PK of inhaled RDV in participants with early stage COVID-19. The study will be conducted in 3 parts (Parts A, B, and C).

Parts A and B

[figure not shown]
In Part A, approximately 36 eligible participants will be randomized in a 1:1:1 ratio to receive 1 of the following 3 study treatments administered via facemask:

Treatment Group 1: 31 mg inhaled Remdesivir for Injection formulation daily for 5 days

Treatment Group 2: 31 mg inhaled Remdesivir for Injection formulation daily for 3 days followed by PTM daily for 2 days

Treatment Group 3: PTM daily for 5 days

Part A

[figure not shown]
In Part B, if supported by Phase 1a data in healthy volunteers, an additional 36 eligible participants may be randomized in a 1:1:1 ratio to receive 1 of the following 3 study treatments administered via facemask:

Treatment Group 4: 62 mg inhaled Remdesivir for Injection formulation daily for up to 5 days

Treatment Group 5: 62 mg inhaled Remdesivir for Injection formulation daily for up to 3 days followed by PTM through Day 5

Treatment Group 6: PTM daily for 5 days

Part B

In Parts A and B, at in-clinic screening, after the participant has provided informed consent, assessments will include but are not limited to the following: demographic and baseline characteristics, medical history, and concomitant medications will be documented. Body weight and height will be measured. A urine pregnancy test will be performed for women of childbearing potential. Vital signs including heart rate, temperature, blood pressure, respiration rate and SpO₂ will be recorded. A complete physical examination will be performed.

[figure not shown]
Participants with PCR-confirmed COVID-19 who enroll in the study will return to clinic daily on Days 1 through 5 for study treatment administration and clinical assessments. Participants will return to clinic on Days 7 and 14 for follow-up clinical assessment and undergo a Day 28 follow-up which may be completed by telephone.

Part C

Part C of the study will include an expanded safety and efficacy assessment of an additional 80 participants. Participants in Part C will be enrolled after review of preliminary safety data from Parts A and B through at least Day 7. Approximately 80 eligible participants will be randomized in a 3:1 ratio to receive 1 of the following 2 study treatments administered via mouthpiece:

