6.1.3. Analysis of the Primary Efficacy Endpoint

DAVG₇ in SARS-CoV-2 viral load will be summarized by treatment group using descriptive statistics in Parts A, B and C. For Part C, DAVG₇ in SARS-CoV-2 viral load will be compared between the RDV and PTM groups using analysis of covariance (ANCOVA) with baseline viral load included in the model as a covariate. Due to small sample sized in Parts A and B, no comparison test will be applied.

The following summary tables will be provided by treatment group:

- DAVG₇ in SARS-CoV-2 viral load based on nasopharyngeal swab samples
- DAVG₇ in SARS-CoV-2 viral load based on oropharyngeal swab samples
- DAVG₇ in SARS-CoV-2 viral load based on saliva samples

After checking that the Part A, Part B, and Part C data are poolable with regard to demographic and baseline characteristics, DAVG₇ in SARS-CoV-2 viral load will be analyzed by the pooled groups outlined in Section 3.2 and comparison will be done using ANCOVA with baseline viral load as the covariate.

The mFAS will be the primary analysis set for evaluation of DAVG₇ in SARS-CoV-2 viral load. A by-participant listing for DAVG₇ in SARS-CoV-2 viral load will be provided. Descriptive statistics will be provided for DAVG₇ in SARS-CoV-2 viral load by treatment group for each of the subgroups defined in Section 3.4.

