Time to negative SARS-CoV-2 viral load, participants are censored at the last assessment day and participants are required to have at least one postbaseline assessment to be included in the analysis.

Time to alleviation of baseline COVID-19 symptoms:

- For overall baseline symptom alleviation, participants are censored at the last assessment day that at least one of the baseline symptoms were assessed.
- For baseline symptom alleviation for each domain, participants are censored at the last assessment day that at least one of the baseline symptoms within that domain were assessed.

14) For 95% CI of KM%, log-log transformation method is adopted.

15) Hazard ratio for time to alleviation

The following SAS code will be used to compute hazard ratio (HR) and its 95% CI:

```
proc phreg;  
  class trt01pn;  
  model days*censor(0) = trt01pn / rl;  
  run;
```

16) Graded Laboratory Abnormalities Summary

The following labels will be used for laboratory abnormalities and Grade 3 or 4 laboratory abnormalities summary tables and listings:

Battery	Lab Test Label Used in I-labtox Listing	Toxicity Direction	Lab Test Label Used in t-labtox Table
Hematology	Hemoglobin	Decrease	Hemoglobin (Decreased)
	Lymphocytes	Decrease	Lymphocytes (Decreased)
	Neutrophils	Decrease	Neutrophils (Decreased)
	Platelets	Decrease	Platelets (Decreased)
	WBC	Decrease	WBC (Decreased)
Chemistry	Albumin	Decrease	Albumin (Decreased)
	Alkaline Phosphatase	Increase	Alkaline Phosphatase (Increased)
	ALT	Increase	ALT (Increased)
	AST	Increase	AST (Increased)
	Bicarbonate	Decrease	Bicarbonate (Decreased)
	Corrected Calcium	Increase	Corrected Calcium (Hypercalcemia)
	Corrected Calcium	Decrease	Corrected Calcium (Hypocalcemia)
	Creatine Kinase (CK)	Increase	Creatine Kinase (Increased)
	Creatinine	Increase	Creatinine (Increased)
	Creatinine Clearance	Decrease	Creatinine Clearance (Decreased)
	Direct Bilirubin	Increase	Direct Bilirubin (Hyperbilirubinemia)
	Lipase	Increase	Lipase (Increased)
	Magnesium	Decrease	Magnesium (Hypomagnesemia)
	Phosphate	Decrease	Phosphate (Hypophosphatemia)
	Serum Glucose (Fasting)	Increase	Serum Glucose (Fasting, Hyperglycemia)
	Serum Glucose (Nonfasting)	Increase	Serum Glucose (Nonfasting, Hyperglycemia)
	Serum Glucose	Decrease	Serum Glucose (Hypoglycemia)
	Serum Potassium	Increase	Serum Potassium (Hyperkalemia)
	Serum Potassium	Decrease	Serum Potassium (Hypokalemia)
	Serum Sodium	Increase	Serum Sodium (Hypernatremia)
	Serum Sodium	Decrease	Serum Sodium (Hyponatremia)

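### The log-log interval for hospitalization and MAV/death does not exist in a zero-event arm, and the log-rank p-values for these endpoints are unreliable at some very small event counts

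*SAP*

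**What the plan says.** SAP 6.2.1 estimates three Day 28 endpoints by Kaplan-Meier and compares arms by log-rank. All-cause MAV or death is "compared among 3 treatment groups in Part A and Part B and between the 2 treatment groups in Part C using a log-rank test". COVID-19 related MAV or death is "analyzed using the same method as used for composite endpoint of all MAVs or all-cause death by day 28". Hospitalization "will be estimated using the Kaplan-Meier method and compared among treatment groups using a log-rank test". SAP Appendix 2 item 14 then fixes the interval: "For 95% CI of KM%, log-log transformation method is adopted". For COVID-19 related MAV or death there is also an optional pooled analysis: "a summary by pooled RDV and Pooled PTM may be provided and compared using CMH method including Part as strata in the model".

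The arms are small. SAP 1.3 states "In Part A, approximately 36 eligible participants will be randomized in a 1:1:1 ratio", and Part B has the same size and ratio, so six arms have about 12 participants each. For Part C, "Approximately 80 eligible participants will be randomized in a 3:1 ratio", which is about 60 remdesivir (RDV) and 20 placebo (PTM).

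For the primary endpoint the SAP declines to test in the small parts (6.1.3): "Due to small sample sized in Parts A and B, no comparison test will be applied". Protocol 8.5.2 names no test for the three endpoints. It plans Kaplan-Meier estimates of MAV or death in Part C only, and a summary of hospitalization by group. Neither document gives a rule for zero events, a minimum event count for testing, or an exact alternative.

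**The concern.** These are the outcomes most likely to be rare. Eligibility requires SpO2 above 94% on room air and excludes participants who need oxygen or hospitalization (Protocol 4.2 and 4.3). In arms of 12 or 20, an arm with no hospitalization is quite possible. The log-log method then yields nothing, so the table would carry 0% with a blank or a program default where the uncertainty should be, although 0/12 is compatible with a true rate above one in four.

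The log-rank test has a related weakness. Its chi-square reference is a large-sample approximation, and with two or three events the p-value can fall on the wrong side of 0.05. The SAP accepts that Parts A and B are too small to test a continuous viral-load endpoint, then tests sparser outcomes in the same arms. A zero-event RDV arm without an interval, next to a small p-value resting on two placebo events, would be easy to over-read.

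**Working it through.** The documents give no event rate, power or event count, so there is no planned figure to reproduce. Arm sizes come from SAP 1.3: 36/3 = 12 in each of six arms, and 80 at 3:1 = 60 and 20. Assumptions: Day 28 event rates of 1% to 20%, equal across arms; distinct event times; no censoring before the last event; a two-sided 0.05 threshold.

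**1. The log-log interval.** The limits are S^exp(±1.96·SE), with SE = √(Greenwood sum)/|log S|. With no events S = 1, so log S = 0, log(−log S) is undefined and the Greenwood sum is 0. There is no interval. With one event it exists: the event percentage runs from 1.2% to 46.1% (1/12), 0.7% to 30.5% (1/20) and 0.2% to 11.2% (1/60).

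The exact (Clopper-Pearson) upper limit for 0/n is 1 − 0.025^(1/n):

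| n | Upper 95% limit |
|---|---|
| 12 | 26.5% |
| 20 | 16.8% |
| 60 | 6.0% |

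**2. How often an arm has no events.** For one endpoint, P(at least one of eight arms) = 1 − [1−(1−p)^12]^6 · [1−(1−p)^20] · [1−(1−p)^60].

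| Assumed rate p | Any of eight arms | Within one part of 12/12/12 | Within Part C |
|---|---|---|---|
| 5% | 99% | 90% | 39% |
| 10% | 88% | 63% | 12% |
| 20% | 36% | 19% | 1% |

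If a whole part has no events, the log-rank statistic is undefined too. At p = 1% that happens with probability 0.99^80 = 45% in Part C and 0.99^36 = 70% in a part of 36.

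**3. Log-rank against its exact permutation p-value.**

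Part C, two events, both PTM. Expected = 20/80 + 19/79 = 0.4905. Variance = 0.1875 + 0.1827 = 0.3702. Chi-square = (2 − 0.4905)²/0.3702 = 6.16, p = 0.013. Exact: C(20,2)/C(80,2) = 190/3160 = 0.060.

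A 12/12/12 part, three events in one arm. Expected = 12/36 + 11/35 + 10/34 = 0.9417. Variance = 0.6453. Chi-square = (3 − 0.9417)²/0.6453 = 6.56 on 2 df, p = 0.038. Exact: 3·C(12,3)/C(36,3) = 660/7140 = 0.092.

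In both cases the reading at 0.05 changes. Enumerating all event orders in Part C gives:

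| Part C events | Log-rank p | Exact p |
|---|---|---|
| 2, all PTM | 0.013 | 0.060 |
| 3, all PTM | 0.002 | 0.014 |
| 2, all RDV | 0.41 | 0.81 |
| 5, all RDV | 0.19 | 0.32 |
| 8, all RDV | 0.092 | 0.18 |
| 11, all RDV | 0.045 | 0.057 |

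When all events fall in one arm, the log-rank p-value is too small whichever arm it is. With 10 or fewer events, no pattern against RDV reaches 0.05; every result that crosses it favours RDV.

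**4. Overall error.** Given a fixed event count, the log-rank rejection rate exceeds 5% at a few counts (Part C: 6.0% at 2 events, 6.2% at 7; 12/12/12: 9.2% at 3, 6.3% at 5). Averaged over counts in 40,000 simulated trials per scenario at rates of 1% to 20%, it is 1.0% to 4.9% in Part C and 0.04% to 4.8% in Parts A and B.

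**The case against.** The case against acting has real force on the test half.

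- **Overall type I error.** A reader might infer that the log-rank test is anti-conservative overall. It is not: at the assumed rates its size stays at or below about 5%. The fault lies at particular counts.
- **Direction.** A reader might infer that only p-values favouring RDV are too small. Those with every event in the RDV arm are too small as well; they do not cross 0.05 until 11 events.
- **Switching to an exact log-rank.** A reader might expect this simply to remove overstatement. In Part C it raises the conditional rejection rate from 1.3% to 4.6% at 5 events, 3.2% to 4.5% at 6, and 2.1% to 5.0% at 8, every added rejection favouring RDV. With 7 events, 4 of them PTM, the exact p runs from 0.011 to 0.062 by event order and is below the log-rank p in 18 of 35 orders. At 11 events, all RDV, the switch takes a result against RDV from 0.045 to 0.057.
- **Day 28 denominators.** Restricting the analysis to participants with known Day 28 status would be wrong. Final contact has a window of ±5 days (Protocol 6.5 and 6.8), and SAP 6.2.1 censors event-free participants at the earlier of Day 28 and last study day. Dropping those contacted on Days 23 to 27 while keeping early events would bias the proportions upward.
- **Stakes.** These are secondary endpoints in an unpowered, largely descriptive study with no multiplicity adjustment. One event rate for all three endpoints is crude, since all-cause MAV covers any in-person medical visit.

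All of this stands, and it argues against a wholesale swap of tests. None of it supplies an interval for a zero-event arm, or a reason to test in arms of 12 when 6.1.3 declines to.

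**Conclusion.** The interval defect is certain: it follows from the formula and needs no assumption. How often it bites depends on event rates that the documents do not give. At 5% to 10% at least one zero-event arm is very likely (99% to 88%), and at 20% it is still about one in three (36%). The information lost is large in the small arms.

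The p-value defect is real but narrow. It changes the reading at 0.05 for two placebo events in Part C and for three events in one arm of a 12/12/12 part. These figures rest on the planned sizes, distinct event times and no early censoring. The documents do not support a claim that the tests fail in general or inflate false positives overall.

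Testing these endpoints in Parts A and B is also inconsistent with the SAP's own reasoning in 6.1.3, and goes beyond Protocol 8.5.2.

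**What to change.** For the two MAV/death composites and hospitalization:

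1. Amend Appendix 2 item 14 to use an exact interval that handles censoring, at least for zero-event arms. The beta product procedure does this and equals Clopper-Pearson when nobody is censored. State that event-free participants whose final contact fell inside the Day 28 window but before Day 28 are censored at that contact and not dropped.
2. Report Parts A and B descriptively, without log-rank p-values, in line with SAP 6.1.3 and Protocol 8.5.2.
3. In Part C, label any log-rank p-value descriptive, and show an exact p-value beside it when events are few. Fix the event count that triggers this in advance.

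The log-log interval and ordinary log-rank test can stay for time to negative PCR and symptom alleviation, where events should be common. No data collection changes. The cost is a few lines of SAP text and some programming, slightly conservative intervals and fewer p-values.
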